10.6.6 Sensitivity Analyses

The method for imputation of missing data for the confirmatory primary efficacy analysis is defined as Last Observation Carried Forward (LOCF). In the case that there is a large amount of missing data, additional methods of imputing missing data will be used to examine the robustness of the treatment effect.

All sensitivity analyses will be conducted on the ITT analysis population and will repeat the confirmatory primary efficacy analysis.

Worst Case

Worst Case analysis will be assessed by imputing missing values as follows:

- The 10th percentile PE value of ExAblate group will be imputed to subjects with missing data in ExAblate group
- The 90th percentile PE value of Sham group will be imputed to subjects with missing data in Sham group

Descriptive statistics with comparison p-value will be provided (**Error! Reference source not found.**).

Best Case

Best Case analysis will be assessed by imputing missing values as follows:

- The 90th percentile PE value of ExAblate group will be imputed to subjects with missing data in ExAblate group
- The 10th percentile PE value of Sham group will be imputed to subjects with missing data in Sham group

Descriptive statistics with comparison p-value will be provided (**Error! Reference source not found.**).

Multiple Imputations

Multiple Imputations analysis will be assessed by creating 10 imputed data sets using the multiple imputation procedure (PROC MI in SAS®). Various baseline characteristics will be considered for the purpose of imputation. Missing PE values will be imputed. The confirmatory primary efficacy analysis will be repeated on each of 10 imputed data sets (**Error! Reference source not found.**). The summarized result (using PROC MIANALYZE in SAS®) will be presented (**Error! Reference source not found.**).

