7.1 Imputation of Confirmatory Primary Efficacy Data

Confirmatory primary efficacy endpoint (PE) is considered missing if either Part A or Part B at 3 Months FU is missing.

Imputation of Part A

Part A is considered missing if at least two out of the three individual rates within item #5 (or #6) are missing. Missing rates at 3 Months FU will be imputed using LOCF method, i.e. rates from 1 Month FU will be carried forward. If a single individual rate is obtained and two other rates are missing, the non-missing rate will be taken as is and will not be imputed.

Imputation of Part B

Part B is considered missing if more than one required items is missing. Missing items at 3 Months FU will be imputed using LOCF method, i.e. items from 1 Month FU will be carried forward. The obtained items will be taken as is and will not be imputed.

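### Where Month 3 is only partly scored, the sensitivity analyses in SAP 10.6.6 replace the whole primary endpoint and ignore the scores obtained, so an imputed value can be infeasible

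*SAP*

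**What the plan says.** SAP 7.1 defines when the endpoint is missing: "Confirmatory primary efficacy endpoint (PE) is considered missing if either Part A or Part B at 3 Months FU is missing". It then defines each part: "Part A is considered missing if at least two out of the three individual rates within item #5 (or #6) are missing"; "Part B is considered missing if more than one required items is missing". So PE can count as missing while the other part is complete, or while some items within the missing part were scored.

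For the primary LOCF analysis, 7.1 protects what was observed. Only the missing rates or items are carried forward from Month 1. For Part B it says "The obtained items will be taken as is and will not be imputed", and Part A has the same rule for a single obtained rate.

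SAP 10.6.6 changes the unit from item to endpoint. Worst Case: "The 10th percentile PE value of ExAblate group will be imputed to subjects with missing data in ExAblate group". Best Case: "The 90th percentile PE value of ExAblate group will be imputed to subjects with missing data in ExAblate group". The Sham arm gets the mirror-image percentiles. For multiple imputation, "Missing PE values will be imputed", and on predictors, "Various baseline characteristics will be considered for the purpose of imputation". Nothing in 10.6.6 retains an observed part or item, conditions on it, or limits the imputed value. The section applies only if missing data are extensive, and it sets no threshold.

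**The concern.** PE is one number per subject, computed from the sum of Parts A and B. Assigning a PE value directly to a partly scored subject therefore drops the Month 3 items that the Core Lab did score. Those items limit how much the subject can have improved or worsened, and an arm percentile or a draw based on baseline data takes no account of that limit.

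What is at stake is how the robustness check can be read. For these subjects the sensitivity analyses differ from LOCF in two ways at once: the assumption about the missing items, and whether observed Month 3 items are used at all. A difference from LOCF, or agreement with it, cannot then be put down to the missing-data assumption alone. The check can also credit a subject with benefit that the subject's own Month 3 scores exclude, or deny benefit that they guarantee.

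**Working it through.** **Scale limits.** The worked example in SAP 6.2.1 gives a maximum of 28 with two Part A rates and five Part B items: 2×4 + 5×4 = 28, which reproduces. Each item therefore runs from 0 to 4. With all three rates, Part A runs from 0 to 12 and a five-item Part B from 0 to 20, so the full limb has 32 points.

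**Feasible PE.** Let b be the Baseline sum, x the observed Month 3 part, and m the maximum of the missing part. With the same items counted at both visits, the divisor in 6.2.1 cancels, and PE lies between 100(b − x − m)/b and 100(b − x)/b.

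**Plausible percentiles.** Section 18 (Potential Benefits) of the long-term follow-up protocol reports Month 3 PE. These results are used only to place the percentiles; normality is an assumption.
- ExAblate: mean 46.9%, 95% CI 40.3% to 53.5%, N=56. SD = 6.6 / t(0.975, 55) × √56 = 24.6. The 10th and 90th percentiles are 46.9 ∓ 1.2816 × 24.6 = 15.3% and 78.5%.
- Sham: mean -0.1%, 95% CI -9.6% to 9.5%, N=20. SD = 9.55 / t(0.975, 19) × √20 = 20.4. The 90th percentile is -0.1 + 1.2816 × 20.4 = 26.1%.

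**Example 1.** Baseline A=6, B=12, so b=18. Month 3 B=12, Part A missing. PE lies between (18 − 12 − 12)/18 = -33% and (18 − 12)/18 = +33%. Best Case assigns 78.5%, which is infeasible. Worst Case assigns 15.3%, which is feasible.

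**Example 2.** Same Baseline, Month 3 B=16. PE cannot exceed (18 − 16)/18 = +11%. Worst Case assigns 15.3%, more benefit than is possible.

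**Other cases.** With b=20 and Part B observed at 2, PE lies between 30% and 90%, so the ExAblate Worst Case value of 15.3% is infeasibly low. With b=20 and a Sham subject's Part B at 16, PE is at most 20%, so the Sham Worst Case value of 26.1% is infeasible. Conflicts also arise at b=16 and b=24. A baseline of 20 is illustrative. It is close to the pilot mean of 20.4 in Protocol 5.4, but that figure is labelled Total CRST, so using it as a Part A + B sum is an assumption.

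**Multiple imputation.** The SAP names no imputation model. Suppose draws were normal with mean 46.9 and SD 24.6, with no useful predictor. The share outside a feasible range L to U is Φ((L − 46.9)/24.6) + 1 − Φ((U − 46.9)/24.6).

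| Baseline sum | Month 3 Part B | Feasible PE | Infeasible draws |
|---|---|---|---|
| 20 | 2 | 30% to 90% | 29% |
| 20 | 4 | 20% to 80% | 23% |
| 20 | 8 | 0% to 60% | 33% |
| 20 | 10 | -10% to 50% | 46% |
| 18 | 12 (Example 1) | -33% to +33% | 71% |

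Example 2, where Part B worsened, would give 1 − Φ((11.1 − 46.9)/24.6), about 93%. The share depends strongly on the case chosen.

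**Shift in the ExAblate mean per subject like Example 1**, measured against the ends of the feasible range:
- Best Case: (78.5 − 33.3)/56 = 0.8 to (78.5 + 33.3)/56 = 2.0 points.
- Worst Case: (15.3 − 33.3)/56 = -0.3 to (15.3 + 33.3)/56 = +0.9 points.

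**The case against.** The best argument on the other side is narrow reach. SAP 6.2.1 already tolerates one missing Part A rate and one missing Part B item, so neither makes PE missing. A wholly missed visit has no Month 3 data to lose. Only subjects with two or more rates or items missing in a part, and something else scored, are affected. Both parts come from the same videotaped assessment, so they may often be present or absent together; that is inference, and the documents give no count. All of this stands and limits the point.

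It is also fair that Best Case is meant to be favourable, that the Worst Case value in Example 1 is feasible, and that using a 10th percentile as the pessimistic bound is a separate matter. None of this answers the case where the assigned value contradicts the subject's own scores.

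A reader might go further and infer that the multiple imputation will produce impossible improvements above 100%. The documents do not support that as a finding, because the SAP specifies no normal model. Under that assumption the share would be small: 1 − Φ((100 − 46.9)/24.6), about 1.6%.

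**Conclusion.** The point holds for partly scored Month 3 assessments. SAP 7.1 keeps scored items and SAP 10.6.6 as written does not, so the sensitivity analyses can assign a PE that the subject's observed scores exclude. In the illustrations, Best Case gives about 78% where at most 33% is possible, and Worst Case gives about 15% where at most 11% is possible. These percentiles rest on the reported confidence interval and a normal approximation; the shares of infeasible draws rest further on an imputation model that the SAP does not state.

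A reader might infer that the confirmatory result is compromised, or that the treatment difference is materially biased. Neither follows. The LOCF primary analysis retains obtained items, the 10.6.6 analyses are conditional, and without the number of partly scored subjects no effect on the treatment comparison can be calculated. Nor is every imputed value infeasible. This is an inexpensive improvement to a secondary robustness check.

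**What to change.** In SAP 10.6.6, state that all Month 3 items obtained are kept and that, where PE is missing under 7.1, only the missing items are imputed, each within 0 to 4. Working by item matters: a part that counts as missing can still contain one scored rate, or several scored Part B items, and imputing the whole part would discard them.

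- **Multiple imputation:** use the observed Month 3 items and the Month 1 scores as predictors alongside baseline characteristics, with a method that respects the item range (for example predictive mean matching), then derive PE by 6.2.1.
- **Worst and Best Case:** keep the 10th and 90th percentile PE, but truncate it to the range feasible given the subject's observed Month 3 items. In Example 1, Best Case becomes 33% and Worst Case is unchanged; in Example 2, Worst Case becomes 11%. Use the untruncated percentile only when no Month 3 item was scored.

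The cost is a few lines of SAP text, slightly longer imputation code, and more variables to impute than a single endpoint.

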10.7 Crossover Stage Analysis

The Crossover stage includes Sham subjects who terminated the Main stage of the study with the reason “Sham subject crossed over ExAblate Arm at Month 3”. According to the protocol, these subjects undergo Active ExAblate treatment and subsequent follow-up assessments, just as defined for the ExAblate group in the Main stage of the study.

All analyses in this section will be presented based on the Crossover analysis population. Results from the Main stage under Sham treatment will be presented in parallel with results under ExAblate treatment during Crossover stage, similarly to presentation of the Main stage results.

Descriptive statistics over time by treatment group will be provided for the following:

- Confirmatory primary and secondary efficacy endpoints
- Additional secondary endpoints

In addition, where appropriate, the following will be provided:

- Graphical presentation over time by treatment group
- Statistical testing to compare:
 - between treatment groups, by visit
 - within each treatment group, comparing Baseline to each follow-up visit
 - between treated and non-treated sides, within each treatment group, by visit

11 Data Listings

[figure not shown]
Data listings will be provided for all data available.

12 Appendix

The following section presents mock tables and figures for Section 10.

12.1 Subject Disposition

Figure 1 Subject Disposition Flow Chart

SF = Screen Failure
